8.14.7. Principal Investigator Documentation Responsibilities

All individual, patient-specific study data will also be entered into a 21 CFR Part 11-compliant electronic data capture (EDC) system on an eCRF in a timely fashion.

All data generated from external sources (eg, laboratory and bioanalytical data), and transmitted electronically to the Sponsor or designee, will be integrated with the patient's eCRF data in accordance with the Data Management Plan. EDC data will be transmitted to the Sponsor at the end of the study as well.

An eCRF must be completed for each patient who signs an ICF, undergoes Screening procedures, and is not a screen failure, in accordance with the eCRF completion instructions. The Sponsor, or CRO, will review the supporting source documentation against the data entered into the eCRFs to verify the accuracy of the electronic data. The PI will ensure that corrections are made to the eCRFs and that data queries are resolved in a timely fashion by the study staff.

The PI will sign and date the eCRF via the EDC system's electronic signature procedure. These signatures will indicate that the PI reviewed and approved the data on the eCRF, data queries, and site notifications.

12 December 2018 Page 52 of 72

8.14.8. **Publications and Data Sharing**

A Clinical Study Report (CSR) will be prepared and provided to the regulatory agency(ies). BeiGene Ltd. (the Sponsor) will ensure that the report meets the standards set out in the ICH Guideline for Structure and Content of Clinical Study Reports (ICH E3). Note that an abbreviated report may be prepared in certain cases.

CONFIDENTIAL

The results of this study will be published or presented at scientific meetings in a timely, objective, and clinically meaningful manner that is consistent with good science, industry and regulatory guidance, and the need to protect the intellectual property of the Sponsor, regardless of the outcome of the study. The data generated in this clinical study are the exclusive property of the Sponsor and are confidential. Authorship will be determined by mutual agreement and all authors must meet the criteria for authorship established by the International Committee of Medical Journal Editors Uniform Requirements for Manuscripts or stricter local criteria. 12

After conclusion of the study and without prior written approval from the Sponsor, the PI may communicate, orally present, or publish in scientific journals or other scholarly media only after the following conditions have been met:

- The results of the study in their entirety have been publicly disclosed by or with the consent of the Sponsor in an abstract, manuscript, or presentation form; or
- The study has been completed for at least 2 years.

No such communication, presentation, or publication will include the Sponsor's confidential information.

The PI agrees to submit all manuscripts or congress abstracts and posters/presentations to the Sponsor prior to submission. This allows the Sponsors to protect proprietary information, provide comments based on information from other studies that may not yet be available to the PI, and ensure scientific and clinical accuracy. The details of the processes of producing and reviewing reports, manuscripts, and presentations based on the data from this trial will be presented in the PI's clinical study agreement.

9. SAMPLE SIZE AND DATA ANALYSIS

9.1. **Determination of Sample Size**

No formal statistical assessment of sample size has been conducted. The sample size chosen for this study is common in human radiolabeled studies and is considered sufficient to achieve the objectives of the study. Up to approximately 10 patients will be enrolled and studied in order that 4 patients complete Part 1 of the study.

12 December 2018 Page 53 of 72

9.2. **Analysis Populations**

9.2.1. **Pharmacokinetic Population**

The PK population will include all patients who received [14C]-pamiparib and have evaluable PK data. Patients will be excluded from the PK summary statistics and statistical analysis if a patient has an AE of vomiting that occurs at or before 2 times median t_{max} .

CONFIDENTIAL

9.2.2. **Safety Population**

The safety population will include all patients who received [14C]-pamiparib.

9.3. **Pharmacokinetic Analyses**

Plasma and urine PK parameters of pamiparib and whole blood and plasma parameters of total radioactivity will be calculated using standard noncompartmental methods.

Additional noncompartmental PK parameters may be determined where appropriate.

Pharmacokinetic parameters will be summarized using descriptive methodology. No formal statistical analysis will be performed.

Descriptive statistics (mean, median, minimum, maximum, standard deviation, geometric mean, and geometric coefficient of variation) will be calculated for all PK parameters and PK concentration data where applicable.

Specification of PK parameters to be presented in the CSR; procedures for accounting for missing, unused, or spurious data; procedures for reporting deviations from the original statistical plan; and selection of patients to be included in the analyses population(s) will be presented in the CSR and/or the Statistical Analysis Plan as appropriate.

All statistical summary calculations will be performed using SAS® Version 9.4 or greater.

9.4. **Safety Analysis**

All AEs will be listed and summarized using descriptive methodology. No formal statistical analysis will be performed. The incidence of AEs will be presented by severity and by relationship with the study drug as determined by the PI (or designee). Each AE will be coded using the Medical Dictionary for Regulatory Activities.

Patient ECOG performance will be reported for the Safety population and will be listed.

9.5. **Interim Analysis**

No interim analyses are planned for this study.

12 December 2018 Page 54 of 72

11. APPENDICES

12 December 2018 Page 56 of 72

CONFIDENTIAL

Protocol Reference: BGB-290-106

Appendix 1: Clinical Laboratory Evaluations

Clinical Chemistry:	Hematology:	Urinalysis:	Serology ^a :
Alkaline phosphatase Alanine aminotransferase Aspartate aminotransferase Albumin Total bilirubin Direct bilirubin Blood urea nitrogen or urea Potassium Sodium Corrected calcium Creatinine Glucose Lactate dehydrogenase Total protein	Hematocrit Hemoglobin Platelet count Red blood cell (RBC) count White blood cell (WBC) count WBC differential: Lymphocytes Neutrophils	Blood Glucose Ketones pH Protein Specific gravity Urobilinogen Microscopic examination	Hepatitis B surface antigen Hepatitis C antibody Hormone Panel – females only Follicle-stimulating hormone (FSH) ^b Serum pregnancy test (human chorionic gonadotropin) ^c Urine pregnancy test ^d

CONFIDENTIAL

Protocol Reference: BGB-290-106

12 December 2018 Page 57 of 72

a. Only analyzed at Screening.

b. Performed at Screening on postmenopausal females only.

c. Performed at Screening on female patients of childbearing potential.

d. Performed on females of childbearing potential at Day -1 (Part 1) and on Day 1 of each treatment cycle (Part 2). A positive urine pregnancy test will be confirmed with a serum pregnancy test.

Appendix 2: Total Blood Volume

The following blood volumes are the maximum planned to be withdrawn for each patient.

CONFIDENTIAL

Protocol Reference: BGB-290-106

12 December 2018 Page 58 of 72

Part 1:

	Volume per blood sample (mL)	Maximum estimated number of blood samples	Total amount of blood (mL)
Clinical chemistry	4.7	4	18.8
Hematology	2.7	4	10.8
Serology	7.5	1	7.5
Glucose	2.7	4	10.8
Plasma for pamiparib concentration	4	16	64
Whole blood for total radioactivity	2	16	32
Plasma for total radioactivity	6	16	96
Plasma for metabolite profiling and identification	10	11	110
Total:			349.9

CONFIDENTIAL

Protocol Reference: BGB-290-106

Part 2:

	Volume per blood sample (mL)	Maximum estimated number of blood samples per visit	Total amount of blood (mL) per visit
Predose, End-of-	, r. L. ()		, F
treatment, and			
Follow-up visits			
Clinical chemistry	4.7	1	4.7
Hematology	2.7	1	2.7
Glucose	2.7	1	2.7
	Volume per blood sample (mL)	Maximum estimated number of blood samples per cycle	Total amount of blood (mL) per cycle
Cycle 1 and Cycle 2			
Cycle 1 and Cycle 2 Clinical chemistry	4.7	2	9.4
	4.7 2.7	2 2	9.4 5.4
Clinical chemistry			
Clinical chemistry Hematology	2.7	2	5.4
Clinical chemistry Hematology Glucose	2.7	2	5.4
Clinical chemistry Hematology Glucose Cycles 3+	2.7 2.7	2	5.4 5.4

12 December 2018 Page 59 of 72

Protocol Amendment Version 3.0 Covance Study: 8381180 Protocol Reference: BGB-290-106

If extra blood samples are required in Part 1, the maximum blood volume to be withdrawn per patient will not exceed 400 mL. If extra blood samples are required in Part 2, the maximum blood volume to be withdrawn per patient will not exceed 40 mL per cycle.

CONFIDENTIAL

12 December 2018 Page 60 of 72

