3. INVESTIGATIONAL PLAN

3.1. Overall Study Design and Plan

This is an open-label, inpatient study in patients with advanced and/or metastatic solid tumors, which consists of 2 parts: a research phase and a treatment phase.

An overview of the study design for Part 1 and Part 2 is shown in Figure 3 and Figure 4, respectively.

Potential patients will be screened to assess their eligibility to enter the study within 28 days prior to the first dose administration. Re-screening of patients will be allowed per the Principal Investigator's (PI's) discretion. Up to approximately 10 patients will be enrolled to ensure 4 patients complete Part 1 of the study.

The start of the study is defined as the date the first enrolled patient signs an Informed Consent Form (ICF). The point of enrollment occurs at the time of patient number allocation. The end of the study is defined as the date of the last patient's last assessment (scheduled or unscheduled) or follow-up.

[figure not shown]
A Schedule of Assessments is presented in Appendix 4.

12 December 2018 Page 25 of 72

Protocol Amendment Version 3.0 Covance Study: 8381180 Protocol Reference: BGB-290-106

3.1.1. **Study Part 1 (Research Phase)**

Figure 3: **Study Schematic: Part 1**

CONFIDENTIAL

Abbreviation: CRU = Clinical Research Unit.

Patients will be admitted into the Clinical Research Unit (CRU) on Day -1. On the morning of Day 1, patients will receive a single oral dose of 60 mg containing approximately 100 μCi (3.7 MBq) of [¹⁴C]-pamiparib.

Patients will be resident at the CRU until completion of all assessments on Day 7, but may be discharged earlier at the PI's discretion if they meet the following discharge criteria:

Approximately 90% of the radioactive dose is recovered

or

< 1% of the radioactive dose is recovered in urine and feces for 2 consecutive 24-hour collection intervals.

If the discharge criteria have not been met on Day 7, patients may be asked to collect 24-hour excreta samples for up to a further 7 days (up to Day 14) on a non-residential basis. Patients may be required to remain resident at the CRU for longer than 7 days if deemed necessary by the PI to ensure patient safety. If the discharge criteria have not been met by Day 14, the need for additional sample collection will be at the discretion of the PI.

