7.1.1. Pharmacokinetic and Metabolite Blood Sample Collection and Processing

Blood samples will be collected by venipuncture or cannulation at the times indicated in the Schedule of Assessments in Appendix 4 for determination of pamiparib concentration, total

12 December 2018 Page 39 of 72 radioactivity, and metabolite profiling and identification. Procedures for collection, processing, and shipping of blood samples will be detailed in a separate document.

CONFIDENTIAL

Approximately 1 × 2 mL blood sample will be collected for total radioactivity in whole blood and approximately 1×6 mL blood sample will be collected for total radioactivity in plasma. Approximately 1 × 4 mL blood sample will be collected for pamiparib concentration in plasma. Approximately 1 × 10 mL blood sample will be collected for metabolite profiling and identification in plasma.

7.1.2. Pharmacokinetic, Total Radioactivity, and Metabolite Urine and Fecal **Collection and Processing**

Urine will be collected over the time intervals indicated in the Schedule of Assessments in Appendix 4 for determination of pamiparib concentration, total radioactivity, and metabolite profiling and identification. Procedures for collection, processing, and shipping of urine collections will be detailed in a separate document.

Feces will be collected over the time intervals indicated in the Schedule of Assessments in Appendix 4 for determination of total radioactivity, and, where possible, metabolite profiling and identification. If possible, a single baseline fecal sample will be collected between Check-in on Day -1 and dose administration on Day 1. Procedures for collection, processing, and shipping of fecal collections will be detailed in a separate document.

7.1.3. **Emesis Sample Collection**

For patients experiencing emesis within 4 hours following oral dosing, vomitus will be collected. If possible, vomitus from patients experiencing emesis after 4 hours postdose will be collected. All vomitus collected will be stored for possible analysis as deemed appropriate.

7.1.4. **Analytical Methodology**

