Appendix 4: Schedule of Assessment

Schedule of Assessments - Part 1

			Days			
Study Procedures	Screening ^a	-1	1	2-7	7-14 ^b	Part 1 Follow- up Visit ^c
Informed consent	X					
Inclusion/exclusion criteria	X	X				
Demographic data ^d	X					
Medical history/current medical conditions ^e	X					
Alcohol breath test	X	X				7
Serology	X					
Follicle-stimulating hormone ^f	X					
Pregnancy test ^g	X	X				
Height	X					
Body weight	X	X				X
ECOG performance status	X	X	X			
Tumor assessments: CT or	X					
MRI scan	Λ					
Study residency:						
Check-in		X				
Check-out				X^b		
Non-residential visit	X				X	X
Study drug administration:						
[¹⁴ C]-pamiparib (60 mg)			X			
Pharmacokineticsh:						
Blood sampling for pamiparib concentration (plasma) ^{h 1}			X	X	X	
Blood sampling for total radioactivity (whole blood and plasma) ^{h 2}			X	X	X	

12 December 2018 Page 62 of 72

Complete physical

Limited physical examination¹

examination^k

			D/1 E W			
Study Procedures	Screening ^a	-1	1	2-7	7-14 ^b	Part 1 Follow- up Visit ^c
Blood sampling for metabolite profiling and identification (plasma) h 3			X	X		
Urine collection for pamiparib concentration, total radioactivity, and metabolite profiling and identification ^{h 4}			X	X	X	
Fecal collection for total radioactivity and metabolite profiling and identification ^{h 5}			X	X	X	
Safety and tolerability:						
Adverse event recording	X	X	X	X	X	X
Prior/concomitant medication monitoring	X	X	X	X	X	X
Clinical chemistry, hematology, and urinalysis	X	X		X (Day 5)		X
Vital signs ⁱ	X	X	X	X (Day 5)	X	X
12-lead electrocardiogram ^j	X	X	X	X (Day 5)		X

CONFIDENTIAL

X

Protocol Reference: BGB-290-106

Abbreviations: CT = computed tomography; ECG = electrocardiogram; ECOG = Eastern Cooperative Oncology Group; MRI = magnetic resonance imaging; QTc(F) = QT interval corrected for heart rate using Fridericia's formula.

a. Screening: Screening period extends from Day -28 to Day -2. The Screening assessments must be performed within 28 days before dosing.

X

X

b. **Discharge:** Patients can be discharged on Day 7, or before at the discretion of the PI if the discharge criteria are met: approximately 90% mass balance recovery, or < 1% of total dose recovered in urine and feces for 2 consecutive 24-hour collection intervals. If the discharge criteria have not been met on Day 7, patients may be asked to collect 24-hour excreta samples for up to 7 days on a non-residential basis.

X

X (Day 5)

X

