c. Follow-up visit: to occur within 7 days of Discharge (if on Day 7 or before), or final non-residential visit (if discharge criteria have not been met by Day 7). If the patient is discontinued from the study, a Follow-up visit should occur within 7 days after dosing, and subjects will attend a Safety Follow-up visit approximately 30 days after the last day of study drug administration or before initiation of new anticancer therapy, whichever occurs first. This visit may occur later than 7 days

12 December 2018 Page 63 of 72

after discussion with the Medical Monitor for specific circumstances, such as prolonged hospitalization. An ECG does not need to occur at the End-of-Treatment visit if one was performed within 14 days prior to the visit. This visit will count as the patient's End-of-Treatment visit.

CONFIDENTIAL

Protocol Reference: BGB-290-106

- d. **Demographics:** Date of birth, gender, ethnicity, and race must be recorded.
- e. Medical History/Current Medical Conditions: General and disease-specific medical history including a history of past and current medical conditions must be recorded at Screening.
- f. Follicle-stimulating hormone: conduced in postmenopausal females only.
- g. **Pregnancy test (in female patients of childbearing potential):** Performed in serum at Screening and in urine at all other times. A positive urine pregnancy test will be confirmed with a serum pregnancy test.
- h. PK sample timepoints:
 - Blood sampling for pamiparib concentration (plasma): Predose and 0.25, 0.5, 1, 1.5, 2, 2.5, 3, 6, 12, 24, 48, 72, 96, 120, and 144 hours postdose. If patient does not meet discharge criteria by Day 7, additional samples may be collected every 24 hours after Day 7.
 - Blood sampling for total radioactivity (plasma and whole blood): Predose and 0.25, 0.5, 1, 1.5, 2, 2.5, 3, 6, 12, 24, 48, 72, 96, 120, and 144 hours postdose. If patient does not meet discharge criteria by Day 7, additional samples may be collected every 24 hours after Day 7.
 - ³ **Blood sampling for metabolite analysis (plasma):** 0.5, 1, 2, 6, 12, 24, 48, 72, 96, 120, and 144 hours postdose.

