Safety and tolerability:	e2 59	۵.	197		40. 40.	
Adverse event recording	X	X	X	X	X	X
Prior/concomitant medication	X	X	X	X	X	X
Clinical chemistry and hematology	X	X	X	X	X	X^1
Urinalysis	X	X			X	g
Vital signs ⁱ	X	X	X	X	X	
12-lead electrocardiogram ^j	X				X	
Limited physical examination ^k	X	X		X	X	X

CONFIDENTIAL

Protocol Reference: BGB-290-106

Abbreviations: CT = computed tomography; ECG = electrocardiogram; ECOG = Eastern Cooperative Oncology Group; MRI – magnetic resonance imaging; QTc(F) = QT interval corrected for heart rate using Fridericia's formula.

- a. **Predose visit:** The Follow-up visit for Part 1 may be used as the predose visit for Part 2 if it occurs ≤ 7 days prior to the start of pamiparib treatment in Part 2. In this event, assessments only need to be conducted once.
- b. Cycle 3+: Cycles will continue as long as the patient is experiencing clinical benefit, or until occurrence of progressive disease (PD), unacceptable toxicity, pregnancy, death, withdrawal of consent, lost to follow-up, major protocol violation which in the opinion of the Sponsor would have significant impact on the study or its outcome, start of new anticancer therapy, withdrawal by the PI, or study termination by Sponsor.
- c. Cycle 1, Day 1: Assessments will be conducted prior to first dosing in Part 2.
- d. End-of-treatment visit: To occur within 7 days after the last day of study drug administration. A visit should be scheduled as soon as possible, but may occur later after discussion with the Medical Monitor for specific circumstances, such as prolonged hospitalization. An ECG does not need to occur at the End-of-Treatment visit if one was performed within 14 days prior to the visit.

12 December 2018 Page 65 of 72

e. **Safety Follow-up visit:** Approximately 30 days after the last day of study drug administration or before initiation of new anticancer therapy, whichever occurs first; a safety follow-up will occur with the outlined safety assessments. If new anticancer therapy is initiated before this safety follow-up, a safety follow-up should be scheduled as soon as possible. Clinical laboratory evaluations are only required if the patient had an ongoing clinical laboratory abnormality at the previous visit that the Principal Investigator considered to be related to study drug. For patients who do not want to or cannot return to the clinic for the safety follow-up, the patient should be contacted by telephone for a review of adverse events.

CONFIDENTIAL

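### Does the Part 1 blood-volume table in Protocol Appendix 2 understate the maximum by leaving out the optional draws after Day 7?

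*Protocol*

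**What the plan says.** **Blood volume.** Appendix 2 of the Protocol introduces its table with "The following blood volumes are the maximum planned to be withdrawn for each patient". The Part 1 rows total 349.9 mL. Below the tables comes the second tier: "If extra blood samples are required in Part 1, the maximum blood volume to be withdrawn per patient will not exceed 400 mL".

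Section 7.1.1 gives the volume of each draw, for example "1 × 4 mL blood sample will be collected for pamiparib concentration in plasma", with 2 mL for whole-blood radioactivity and 6 mL for plasma radioactivity. The Part 1 schedule in Appendix 4 marks pamiparib and radioactivity bloods in the Day 7-14 column, and footnotes h1 and h2 each say: "If patient does not meet discharge criteria by Day 7, additional samples may be collected every 24 hours after Day 7". Section 3.1.1 adds: "If the discharge criteria have not been met by Day 14, the need for additional sample collection will be at the discretion of the PI".

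The schedule row "Clinical chemistry, hematology, and urinalysis" is marked at Screening, Day -1, Day 5 and the Part 1 Follow-up visit. Footnote c times that visit "to occur within 7 days of Discharge (if on Day 7 or before), or final non-residential visit". Footnote a of the Part 2 schedule adds, subject to a 7-day window: "The Follow-up visit for Part 1 may be used as the predose visit for Part 2".

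**Home excreta collection.** Protocol Section 3.1.1, footnote b of the Part 1 schedule and SAP Section 6.1 allow collection to continue after Day 7 when the discharge criteria are unmet. Either criterion is enough for discharge: about 90% of the dose recovered, or under 1% recovered in each of two consecutive 24-hour intervals. Footnotes h4 and h5 allow home collection of urine and feces when 90% has not been recovered in the unit, and do not mention the 1% criterion.

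**The concern.** A table headed as the planned maximum would be expected to include every draw printed in the schedule, and this one stops at 144 hours. If a site took full daily sets to Day 14, it would exceed the protocol's own limit on blood loss. Footnotes h1 and h2 do not point to that limit, and no visible passage says which draws to drop.

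The order of events sharpens the worry. The Follow-up labs come after all the extension draws. A site that tracks only blood already taken could believe it was under 400 mL after a fifth set, then find that the scheduled safety labs take it over. Those labs may also serve as the predose check for Part 2.

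For excreta, urinary and fecal recovery of radioactivity is a primary objective with four planned completers. SAP Section 10.3.1 sums urinary excretion over the whole collection period, so the rule for extending collection bears on the result.

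**Working it through.** **1. Reproduce the stated total.** Inputs are volume per sample times number of samples, from the Part 1 table in Appendix 2:

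| Row | mL × n | Total (mL) |
|---|---|---|
| Clinical chemistry | 4.7 × 4 | 18.8 |
| Hematology | 2.7 × 4 | 10.8 |
| Serology | 7.5 × 1 | 7.5 |
| Glucose | 2.7 × 4 | 10.8 |
| Plasma pamiparib | 4 × 16 | 64 |
| Whole-blood radioactivity | 2 × 16 | 32 |
| Plasma radioactivity | 6 × 16 | 96 |
| Plasma metabolites | 10 × 11 | 110 |
| **Sum** | | **349.9** |

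This matches the Protocol. The counts of 16 and 11 equal the timepoints listed in footnotes h1 to h3 through 144 hours, so no draw after Day 7 is included.

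**2. Headroom for optional draws.** A full set is 4 + 2 + 6 = 12 mL. Headroom is 400 − 349.9 = 50.1 mL, and 50.1 / 12 = 4.175, so four full sets fit.

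| Full sets after Day 7 | Total (mL) | Within 400 mL |
|---|---|---|
| 1 | 361.9 | yes |
| 3 | 385.9 | yes |
| 4 | 397.9 | yes |
| 5 | 409.9 | no (9.9 over, 2.5%) |
| 7 (daily to Day 14) | 433.9 | no (33.9 over, 8.5%) |

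Footnotes h1 and h2 are separate permissions, so partial sets are possible. Seven pamiparib-only draws give 349.9 + 7 × 4 = 377.9 mL. Radioactivity-only draws are 2 + 6 = 8 mL each: six give 397.9 mL and seven give 405.9 mL.

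**3. The Follow-up labs.** One safety set is 4.7 + 2.7 + 2.7 = 10.1 mL. It is counted four times, matching the four scheduled visits. Before the Follow-up visit and any extension draw, the blood taken is 349.9 − 10.1 = 339.8 mL.

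- After four sets: 339.8 + 48 = 387.8 mL; with Follow-up labs, 397.9 mL.
- After five sets: 339.8 + 60 = 399.8 mL; with Follow-up labs, 409.9 mL.

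The overshoot therefore needs a site that leaves out a scheduled visit already counted in the table. Read from the table, the headroom is 50.1 mL and the fifth set is visibly excluded.

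**4. Entry to Part 2.** Section 3.1.2 requires safety assessments within 7 days before Part 2 treatment, at the Part 1 Follow-up visit or at a separate one. The Part 2 schedule marks chemistry and hematology at the predose visit, and the Part 2 table in Appendix 2 budgets 4.7 + 2.7 + 2.7 = 10.1 mL for it. If the Part 1 Follow-up labs were omitted, the predose labs would still be required.

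**5. Excreta condition, side by side.**

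| Patient at Day 7 | Section 3.1.1, footnote b, SAP 6.1 | Footnotes h4/h5 |
|---|---|---|
| At or above 90% recovered | no extension | no extension |
| Below 90%, no two consecutive intervals under 1% | may extend | may extend |
| Below 90%, two consecutive intervals under 1% | criteria met, no extension | may collect |

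Apart from the small difference between about 90% and at least 90%, only the last row differs. The closing line under footnote h stops sampling for patients who meet the criteria and are discharged before Day 7. That leaves mainly a patient still resident at Day 7. If combined daily output stays below 1% of dose, seven further days add less than 7 × 1% = 7% of dose.

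**The case for a change.** The strongest opposing case is that draws printed in the schedule are foreseeable, so a table of maxima should count them. The permission in h1 and h2 has no stated number, and Section 3.1.1 leaves sampling after Day 14 open. Daily full sets cannot all be taken under the limit, and the reader has to work that out. A single rule should also govern excreta collection when recovery is a primary objective.

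Part of this stands. The footnotes do not refer to the limit, no order of omission is visible (collection procedures are in a separate document), and h4 and h5 give only half of the condition in footnote b.

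The rest does not carry through. Appendix 2 has two tiers, and draws that may be taken only when discharge criteria are unmet belong in the second. The limit is per patient for Part 1 with no end day, so it already covers draws after Day 14. The figure of 433.9 mL is barred by the Protocol's own text. The seven-day period in Section 3.1.1 refers to excreta, and nothing requires seven blood sets. The excreta passages are both permissive, so no site faces conflicting obligations, and the Day 7-14 column heading carries footnote b with both criteria.

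**Conclusion.** No change to the plan is needed. The 349.9 mL total is correct for the timed samples, and the 400 mL limit governs the optional draws: four full sets fit and a fifth does not. A site that follows the text stays within the limit with the Follow-up labs included.

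The count of four assumes all three sample types at each draw and no other unscheduled blood. One unplanned 10.1 mL safety set would reduce it to three (385.9 + 10.1 = 396.0 mL, against 397.9 + 10.1 = 408.0 mL with four). The limit still works in that case; it simply leaves fewer late samples. SAP Section 10.3 names no parameter that requires daily blood samples after Day 7.

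The excreta mismatch is an abbreviated footnote. It affects only patients below 90% recovery who have already had two consecutive intervals under 1%, mainly those resident to Day 7. The amount at issue is below 7% of dose, provided daily output stays under 1%, and would not make the recovery results unsound. Cross-references in the footnotes would make the text easier to read, but no planned analysis or stated figure depends on them.
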